## **8. SAFETY**

Unless otherwise specified, safety analyses are based on the Safety Set.

### **8.1. Exposure**

#### **8.1.1. Extent of Exposure**

Exposure duration (in days) and total nightly dose (in g/night) will be summarized as continuous variables.

#### **8.1.2. Treatment Compliance**

XYWAV treatment compliance will be calculated as the ratio of treatment consumed divided by the expected consumption, expressed as a percentage:

$$\text{Compliance (\%)} = \frac{\text{Volume of solution taken during the intervention period}}{\text{Volume of solution that should have been taken during the intervention period}} \times 100\%$$

The numerator is the volume of solution taken during a study period (i.e., total dispensed – total returned). The denominator is the total daily volume that should have been taken during the intervention period according to the prescribed daily dose(s).

$$\text{Volume That Should Have Been Taken (ml)} = \text{Dose (g)} * 0.5 \text{ ml/g}$$

Treatment compliance during the intervention period will be summarized as a continuous variable and summarized by category (<75%, 75-125% and >125%).

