**Table 2: Overall Study Design**

Study Phase	Phase 3/Phase 4
Clinical Indication	Narcolepsy
Study Type	Interventional
Type of Design	Open-label, single-arm switch study
Type of Control	None
Study Blinding	N/A, open-label
Population	The study will include participants 18 to 70 years of age with a diagnosis of Type 1 or Type 2 narcolepsy that meets ICSD-3 criteria or DSM-5 criteria, who have been receiving 6 to 9 g/night (inclusive) of twice-nightly high-sodium oxybate for $\geq 6$ consecutive weeks [REDACTED].
Number of Study Sites	Up to approximately 60 study sites worldwide are anticipated to enroll participants in this study.
Number of Participants	This study will use a sequential design in which the sample size is not fixed, and data will be evaluated during a planned interim analysis to determine the final study sample size. Thus, the sample size is presented as a range that depends on the results of the interim analysis. The sample size also accounts for a 60% screen failure rate after enrollment (ie, signing the ICF) during the Screening Period and assumes a 15% discontinuation/withdrawal rate during the Intervention Period.

	Based on these assumptions, approximately 170 (up to approximately 230) study participants will enroll to enable a minimum of 67 (up to approximately 91) to initiate treatment with the study intervention (ie, switch to XYWAV) and to capture complete data (both during the Screening Period and at the EOT Visit) for a minimum of 57 participants (up to approximately 77).
Duration of Participation	
The study includes the following study periods: a Screening Period (up to 3 weeks), an Intervention Period (approximately 6 weeks, initiated by the switch from twice-nightly high-sodium oxybate to XYWAV) that includes approximately 6 weeks of treatment, an EOT Visit, and a Safety Follow-up Visit (at least 2 weeks after the last dose of study intervention). The study duration for each participant will be up to approximately 11 weeks.
 
From the start of the Intervention Period through the Safety Follow-Up Visit, each participant will take approximately 8 weeks to complete their study participation.

Treatment Duration	Approximately 6 weeks

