Visit Frequency	
Participants will attend up to 8 scheduled visits during this study (visit schedules are specified in the SoA [Section 1.3]).
 
This will be a hybrid study to allow participants to enroll either virtually (decentralized participants) or at an investigational site (site-based participants).
 
Decentralized participants are participants who are enrolled virtually and who will not have any assessments performed physically at an investigational site.
 
Site-based participants are participants who are enrolled at an investigational site and will have some assessments performed at that site.
 
For all participants (both decentralized and site-based), some visits will be conducted entirely by telemedicine. For decentralized participants, some assessments will require in-person presence of study personnel at the participant's location. Details are provided in the SoA (Section 1.3).

Number of Treatment Arms	1
Treatment Groups	XYWAV (6 to 9 g/night)
Data Monitoring Committee	
A data monitoring committee is not planned for this study.
 
A steering committee will be assembled for this study.

Abbreviations: DSM-5 = Diagnostic and Statistical Manual of Mental Disorders, Fifth Edition; EOT = End of Treatment; ICF = Informed consent form; ICSD-3 = International Classification of Sleep Disorders - Third Edition; SBP = Systolic blood pressure; SoA = Schedule of Activities.

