AE/SAE reporting		X	X	X	X	X	X	X	X	
Concomitant medications	X	X	X	X	X	X	X	X	X	
Dispense study intervention (XYWAV)		X		X	X		X			
Start XYWAV dosing		X								
Study intervention compliance review				X	X		X	X		Refer to Section 6.5.
Collect post-study intervention narcolepsy treatment information									X	This information will only be collected for participants in the US.

Abbreviations: AE = adverse event; approx = approximately; BP = blood pressure; C-SSRS = Columbia-Suicide Severity Rating Scale; E/D = early discontinuation; EOT = end of treatment; OBPM = office blood pressure measurement; PGIC = Patient Global Impression of Change; PGIs = Patient Global Impression of Severity; SAE = serious adverse event; SFU = safety follow-up; V = visit; WOCBP = woman of childbearing potential.

a Unscheduled visits will be needed (eg, for repeating the 24-hour BP assessment [if needed; up to 2 additional times], returning the BP recording device, or another reason per the investigator's discretion). Quality control criteria for 24-hour BP recordings are defined in Section 8.2.1.

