### **6.5. Study Intervention/Treatment Compliance**

Jazz (sponsor) will provide open-label bottles of XYWAV oral solution 0.5 g/mL for the study.

The participant will self-administer study intervention(s) as directed by study personnel and complete an electronic study intervention dosing diary (refer to Section 8.2.3) as specified in the SoA (Section 1.3). Completeness of the study intervention dosing diary will be discussed and assessed by study personnel. Study personnel will also counsel participants who have not been compliant with dosing and diary completion.

Treatment compliance will be measured (either by study personnel during a site visit or by the participant during a telemedicine visit) and recorded on the drug accountability log by study personnel. A designated staff member will also record the number of bottles and the volume of study intervention dispensed and returned.

Suspected misuse or potential abuse of the study intervention (XYWAV) should be investigated, and participant counseled when there is a discrepancy of  $\geq 30$  mL between the returned volume and the expected returned volume.

A record of the quantity of study intervention dispensed to and administered by each participant must be maintained and reconciled with study intervention and compliance records. Intervention start and stop dates, dosage information including dose and regimen adjustments, and any deviation(s) from the prescribed treatment regimen or dosage (including overdosing, described in Section 6.8) should be recorded in the eCRF.

Sites are responsible for identification and documentation of missing bottles during the study. Unused study intervention (partially used, unused, or empty bottles) will be returned per sponsor instructions. If any bottles have not been returned to the site or designee, the reason must be documented. If bottles are not returned at the final visit, the site must document 3 attempts (where possible, 2 telephone calls and a certified letter to the participant) to retrieve the unreturned bottles.

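### Compliance in SAP 8.1.2 scores unreturned solution as taken, no visit is marked for reconciling the V7 supply, and the dose-to-volume factor is inverted (minor)

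*SAP*

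**What the plan says.** SAP 8.1.2 defines compliance as volume taken over volume that should have been taken, as a percentage. On the numerator it says: "The numerator is the volume of solution taken during a study period (i.e., total dispensed – total returned". Nothing there deals with a bottle that is lost, spilled or kept. The denominator converts prescribed dose to volume with a factor of 0.5 ml/g. The result is reported as a continuous variable and in three bands, cut at 75% and 125%.

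Protocol 6.5 says that the sponsor "will provide open-label bottles of XYWAV oral solution 0.5 g/mL for the study". It also foresees missing bottles: "If any bottles have not been returned to the site or designee, the reason must be documented". Three retrieval attempts must be documented when bottles are missing at the final visit. Volumes dispensed and returned are recorded and reconciled, and a gap of 30 mL or more between returned and expected returned volume is to be investigated. The 30 mL rule is not tied to a visit.

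In Protocol Table 3 the row beginning "Dispense study intervention (XYWAV" is marked at V2, V4, V5 and V7. Table 4 is the same, except that the first supply is marked in the Screening column. In both tables the row "Study intervention compliance review" is marked at V4, V5, V7 and E/D and is blank at V8.

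Protocol 9.3.1.1 ends the Intervention Period at the EOT or E/D Visit, whichever comes first. SAP 5.2.2 ends it when XYWAV ends.

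**The concern.** Dispensed minus returned equals intake only if everything not swallowed comes back. Where it does not, the formula treats an unknown returned volume as zero. That is an implicit imputation, always in the favourable direction, although SAP 5.2.4 summarizes data without imputing missing values. A participant who took too little and kept the rest can then move out of the lowest compliance band.

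The V7 supply is the most exposed. It has a purpose, because dosing goes on until an EOT recording passes quality control, with up to two repeats. A review held at V7 cannot measure use of what V7 hands out, and no later review is marked for participants who reach V7.

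The dosing diary covers only about 7 days around each recording (Protocol 8.2.3). For most of the roughly six weeks, bottle accountability is therefore the main scheduled measure of intake, in a study whose result will be read as the effect of that treatment period.

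**Working it through.** **Inputs.** Concentration 0.5 g/mL (Protocol 6.5). Dose: the treatment group entry in Protocol Table 2 begins "XYWAV (6 to 9 g/night". Duration: the same table gives "Intervention Period (approximately 6 weeks, initiated by the switch from twice-nightly high-sodium oxybate to XYWAV", taken here as 42 nights. SAP factor 0.5 ml/g (SAP 8.1.2). Not in the documents: bottle size, volume dispensed per visit, and how often bottles are not returned.

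**1. The plan's own factor.** Volume per gram = 1 / concentration = 1 / 0.5 = 2.0 mL/g. With the oxybate concentration of 0.413 g/mL it would be 1 / 0.413 = 2.42 mL/g. Neither gives 0.5, so the SAP figure is not reproduced. It is the g/mL number carrying mL/g units.

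| | 6 g/night | 9 g/night |
|---|---|---|
| Nightly volume at 2 mL/g | 12 mL | 18 mL |
| 42 nights at 2 mL/g | 504 mL | 756 mL |
| 42 nights at the SAP's 0.5 ml/g | 126 mL | 189 mL |
| Ratio | 4.0 | 4.0 |

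Full adherence therefore reads 400%. The 75% and 125% cuts fall at true intakes of 75/4 = 18.75% and 125/4 = 31.25%. Steps 2 and 3 use 2 mL/g.

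**2. Unreturned solution.** Upward error in points = 100 × unreturned mL / expected mL.

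- 30 mL: 30/504 = 6.0 points at 6 g; 30/756 = 4.0 points at 9 g.
- 100 mL (assumed, for illustration): 100/504 = 19.8 points; 100/756 = 13.2 points. A reported 75% is then a true 75 − 19.8 = 55.2% at 6 g, or 75 − 13.2 = 61.8% at 9 g.
- 0 mL (bottle empty): no error.

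**3. Nights after V7.** Assume 1 to 12 further nights. The upper end is three recordings, each of 1 day plus up to 3 days to device return: 3 × 4 = 12. Volume runs from 1 × 12 = 12 mL to 12 × 18 = 216 mL. As a share of the 42-night volume it is 1/42 = 2.4% to 12/42 = 28.6%. If this volume enters the numerator while the denominator stops at V7, a fully adherent participant reads 102.4% to 128.6%, even with every leftover returned. If both run to the last dose, the error is zero.

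**The case against.** A reader might infer that the V7 supply never gets the misuse check. The documents do not support that. Protocol 6.5 applies its return, reconciliation, retrieval and 30 mL rules to every supply, and none of them stops at V7. A device-return contact follows within 3 days of each recording, and V8 comes after that. Final disposition is also covered in a Pharmacy Manual that is not among these documents. What stands is narrower: no visit is marked for applying these rules to that supply.

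A reader might also infer that every unreturned bottle overstates intake. An empty one adds nothing; only solution left inside counts. Nor can a large typical error be derived by supposing that a whole dispensing interval's supply is both unused and unreturned. The documents give no basis for that, and before V7 such a gap would far exceed the 30 mL trigger at a marked review.

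The period mismatch is only a possibility. Under the SAP's own definition the denominator runs to the end of XYWAV, and either definition works if applied to both parts of the ratio.

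Finally, the consequence is low. Compliance is a descriptive summary in the safety section, does not define the Completer or Effectiveness Set, and enters no efficacy model. The diary and the recorded regimen deviations give other evidence on dosing near the BP recordings. All of this stands and sets the severity.

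**Conclusion.** The point holds as a minor one with three parts.

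- SAP 8.1.2 scores solution in unreturned bottles as taken. The bias is upward only, at 4.0 to 6.0 points per 30 mL (9 to 6 g/night, 42 nights, 2 mL/g). The overall amount cannot be estimated from the documents.
- Neither schedule marks a compliance review after V7 dispensing, and the two definitions of the intervention period leave room to count V7 volume without its nights. That would add 2.4 to 28.6 points under the assumed 1 to 12 extra nights.
- The 0.5 ml/g factor contradicts the 0.5 g/mL product and, applied as written, multiplies every compliance value by four. This is the largest of the three errors, but correcting it leaves the other two in place.

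The primary SBP test does not depend on any of them. Visit assignments were read from column positions in text extracted from PDF and should be confirmed against the laid-out tables.

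**What to change.** 1. **Protocol Tables 3 and 4.** Mark the compliance review at an existing contact after the last dose: the device-return contact at which the EOT recording is accepted, or V8. Reconcile the V7 supply there and apply the Protocol 6.5 discrepancy check to it. Protocol 6.5 already allows compliance to be measured in a telemedicine visit.
2. **SAP 8.1.2, numerator and denominator.** Use the same nights for both, from Day 1 through the last XYWAV dose, and reconcile the period definitions in Protocol 9.3.1.1 and SAP 5.2.2. Do not score unreturned volume as taken: compute compliance from intervals with all bottles returned, and call it not evaluable where there are none. Report the number of participants with unreturned bottles beside the summary, since leaving them out can itself flatter it.
3. **SAP 8.1.2, factor.** Replace 0.5 ml/g with 2 mL/g, to agree with the 0.5 g/mL product. Do this first, because the compliance bands have no meaning until it is done.

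The cost is one mark in each schedule table, a few sentences in the SAP, and some compliance values reported as not evaluable. No new visit is needed.

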**Table 5: Study Treatment/Intervention**

Treatment Arm	Intervention/ Treatment Name	Formulation	Unit Dose Strength(s)	Dosage Level(s)	Route of Administration	Use	Sourcing	Packaging	Labeling	Storage Conditions
1	JZP258 (XYWAV)	Solution	0.5 g/mL (0.413 g/mL oxybate)	XYWAV will be initiated at the dose equivalent (gram-per-gram) to that for prior high-sodium oxybate a twice-nightly regimen (6 to 9 g/night).	Oral	Experimental	Provided centrally by the sponsor	Study intervention medication will be provided in bottles with inserted Press-in Bottle Adapter (and accessories eg, dosing cups and dosing syringe), labeled per country-specific guidelines.  All packaging and labeling operations per current Good Manufacturing Practice and local requirements and regulations.  Child resistant packaging as required.	Open-label	Store at room temperature between 20°C and 25°C (excursions permitted between 15°C and 30°C).

a During the Screening Period, participants will continue to take their own commercial twice-nightly high-sodium oxybate (and any concomitant antiepileptics or stimulants) at the same dose and regimen as prescribed by their healthcare physician prior to enrollment in this study. Participants will use their own supply of twice-nightly high-sodium oxybate (and any other prescribed drugs), which will not be provided separately as part of this study.

The timing for treatment switch from twice-nightly high-sodium oxybate to XYWAV will be scheduled once it has been confirmed that the ambulatory BP assessment during the Screening Period meets minimum data quality standards. Participants will be provided detailed instructions regarding the exact timing for the treatment switch.

The Intervention Period begins on the day of the treatment switch. That night, participants will initiate the switch from twice-nightly high-sodium oxybate to XYWAV, with an immediate gram-for-gram transition. The switch occurs over 1 night. After the switch to XYWAV, the participant should remain on this same dose of XYWAV for the remainder of the study. Modest dose adjustments are permitted if necessary in the opinion of the investigator (Section 6.6 provides additional details).

Participants will also complete a study intervention dosing diary before and after the switch to XYWAV as specified in the SoA (Section 1.3); additional details are provided in Section 6.5.

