## **6.6. Dose Modification**

Participants will switch from twice-nightly high-sodium oxybate to XYWAV with an immediate gram-for-gram switch (as described in Section 6.1). For participants who, in the opinion of the investigator, require a modest adjustment to their XYWAV (up or down by 1.5 g/night), this adjustment may be made during the Intervention Period, provided the participant's total nightly dose is 6 to 9 g/night (inclusive).

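### The SAP compliance formula inverts the product strength, so the expected volume is four times too small and full adherence scores 400%

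*SAP*

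**What the plan says.** SAP Section 8.1.2 defines XYWAV compliance as the volume taken divided by the volume that should have been taken, as a percentage.

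- **Numerator:** "The numerator is the volume of solution taken during a study period (i.e., total dispensed – total returned").
- **Denominator in words:** "The denominator is the total daily volume that should have been taken during the intervention period according to the prescribed daily dose(s").
- **Denominator as a formula:** "Volume That Should Have Been Taken (ml)} = \text{Dose (g)} * 0.5 \text{ ml/g".
- **Reporting:** as a continuous variable, and "summarized by category (<75%, 75-125% and >125"%).

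The protocol states the strength of the solution in two places. Table 5 gives "0.5 g/mL (0.413 g/mL oxybate"), and Section 6.5, on treatment compliance, says the sponsor supplies "open-label bottles of XYWAV oral solution 0.5 g/mL for the study". Section 6.6 allows a modest dose adjustment provided the "total nightly dose is 6 to 9 g/night (inclusive"). The SAP does not state the strength anywhere else, and its modification history through version 3.0 lists no correction to this line.

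**The concern.** Volume equals dose divided by concentration. At 0.5 g/mL the conversion factor is 2 mL per gram, whereas the SAP multiplies grams by 0.5 mL per gram. The line balances dimensionally (g × mL/g = mL), so a units check within the SAP would not catch it. It fails only when set against the strength in the protocol.

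The numerator is a measured volume and carries no matching error, so nothing cancels. A programmer who follows the SAP as signed would produce a wrong percentage for every participant and put nearly all of them in the wrong band. This is the only planned summary that compares volume consumed with volume prescribed. In a single-arm switch study, a reader of the report will want to know whether participants took the product for the six weeks over which the blood pressure change is measured.

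**Working it through.** **Inputs**

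- SAP factor: 0.5 mL/g, multiplied by dose (SAP 8.1.2).
- Strength: 0.5 g/mL (protocol Table 5 and Section 6.5).
- Nightly dose: 6 to 9 g (protocol 6.6); 7.5 g is used as a mid-range value.
- Bands: <75%, 75-125%, >125% (SAP 8.1.2).
- Nights: 42, for approximately 6 weeks of treatment. This is used only to illustrate totals; the ratio does not depend on it.

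**Step 1. Can the SAP factor be reproduced?** From the labelled strength, 1 / 0.5 g/mL = 2 mL/g. From the oxybate moiety at 0.413 g/mL, 1 / 0.413 = 2.42 mL/g. Neither gives 0.5 mL/g.

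**Step 2. Expected volume per night and score for full adherence**

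| Dose (g) | SAP: dose × 0.5 (mL) | From strength: dose / 0.5 (mL) | Score at full adherence |
|---|---|---|---|
| 6 | 3 | 12 | 12 / 3 = 400% |
| 7.5 | 3.75 | 15 | 15 / 3.75 = 400% |
| 9 | 4.5 | 18 | 18 / 4.5 = 400% |

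The factor is 2 / 0.5 = 4 at every dose. Over 42 nights at 9 g, the SAP expects 42 × 4.5 = 189 mL against 42 × 18 = 756 mL, again a ratio of 4.

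**Step 3. What the bands then mean.** The reported score is 4 × true adherence, so each cut-point is divided by 4: 75 / 4 = 18.75% and 125 / 4 = 31.25%.

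| Reported band | True adherence it captures |
|---|---|
| <75% | below 18.75% |
| 75-125% | 18.75% to 31.25% |
| >125% | above 31.25% |

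A participant who took a quarter of the prescribed volume (4.5 of 18 mL at 9 g) scores 100%. One who took a third and one who took all of it both land in >125%.

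**Step 4. Sensitivity to the meaning of grams.** If doses were in grams of oxybate moiety, full adherence would score 2.42 / 0.5, about 484%, and the middle band would hold true adherence of about 15.5% to 25.8%. The error is then larger, in the same direction.

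**Step 5. Summation over nights.** The formula line shows one dose and no sum, while the sentence above it refers to a daily volume and to the whole intervention period. The 400% assumes the sum is taken, which is the only sensible reading when the numerator is a whole-period volume. Taken literally with a single night's dose, 42 nights of full adherence would score 42 × 400% = 16,800%.

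**Step 6. With the corrected line.** Full adherence scores 756 / 756 = 100%, and a quarter of the dose scores 25%, in the <75% band.

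**The case against.** The case on the other side accepts the arithmetic and contests the consequences. Most of it stands.

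- **No inferential result depends on the percentage.** A reader might infer that the error reaches the efficacy results. It does not. The Completer Set (SAP Section 4, protocol 9.2) requires the EOT Visit after six weeks of intervention with an adequate 24-hour recording, and has no compliance threshold. The primary and secondary models, the Effectiveness Set sensitivity analyses, the listed subgroups, the interim rule and the safety endpoints do not use the percentage either.
- **Exposure is described in other ways.** A reader might infer that nothing else in the plan shows whether XYWAV was taken. SAP 8.1.1 summarizes exposure duration and total nightly dose, and SAP 7.3.3 summarizes change in 24-hour urine sodium, which is indirect evidence. The protocol also collects a dosing diary around each 24-hour recording. Only the narrower statement holds: no other planned summary sets volume consumed against volume prescribed.
- **No misuse alarm follows from it.** Scores near 400% could be read as overuse of a controlled product. But protocol 6.5 screens for misuse by a separate rule, a discrepancy of at least 30 mL in returned volume, which does not cite the SAP formula. The percentage triggers no action for any participant.
- **No band is named.** Calling the 75-125% band compliant is a natural reading, but the SAP gives none of the bands a label.
- **The error would be noticed and can be undone.** Adherent participants would cluster near 400%, and the dispensed and returned volumes remain in the data. This is true, but without a written correction the programmer would have to depart from a signed SAP. The banded table also cannot be corrected from its own counts, because the top band mixes true adherence from just over 31.25% upward.

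**Conclusion.** The formula is wrong as written. The expected volume is too small by a factor of exactly 4, independent of dose and duration, provided that doses are summed over nights and grams are on the labelled 0.5 g/mL basis. On the oxybate-moiety basis the factor would be about 4.84. Both planned compliance summaries would misstate adherence for every participant with a non-zero volume taken, and the banded one would lose its meaning.

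The effect is confined to one descriptive exposure output in the safety section. The documents give no ground for extending it to the primary result, the analysis sets, the interim decision or the handling of misuse. Severity: should-fix, before the compliance table is produced.

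**What to change.** Replace the formula line in SAP 8.1.2 with:

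*Volume that should have been taken (mL) = sum over intervention-period nights of [prescribed nightly dose (g) / 0.5 g/mL], equivalently the summed dose × 2 mL/g.*

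This corrects the factor and supplies the summation over nights that the printed line omits. It also handles participants whose dose changes during the period, because each night enters at its own prescribed dose. Keep the three bands.

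The cost is one line in the SAP and one derivation in the analysis program. Because SAP version 3.0 is signed, the change should go through a SAP revision, or be recorded with its rationale as a correction in the CSR. It needs no protocol amendment and no new data.
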